The Immediate Extent of the Hypoalgesic Effect Following Central

Mobilisations to L3, L4 and L5.

October 27th 2023

Study Protocol

Study Design

The design of the study was a randomised, single-blind, repeated measures, cross-over design, performed in a single-centre environment. Ethical approval was gained from the School of Sport and Exercise Science ethics committee at the University of Worcester (ISES2018RF1). Informed consent was gained from each participant before testing.

Sample and Inclusion Criteria

The study included twenty asymptomatic participants (11 females and 9 males); the mean age of the participants was 21.9 years (±2.67, range 20- 30). A health questionnaire (based on the PARQ) was completed by each participant to establish any contraindications they may have to the experimental procedures, namely the application of vertebral mobilisations. No participants were required to be excluded as none of them had consulted their doctor in the last six months, were taking any medication, had an infection in the past two weeks, had no heart, asthma, diabetes, bronchitis, epilepsy or blood pressure issues, had any current muscle or joint injury, were able to train/exercise normally or knew of any other reason that would preclude them from participating.

Data Collection

Each participant was randomly assigned using a random number generator to the order in which their lumbar vertebral levels were mobilised and to the order of each dermatome level tested for the baseline and all three mobilisation interventions.

Before initiating the experimental procedure, the participant's age, height, and weight were recorded. The participant was instructed to lay on their back, on the plinth and had the five locations for dermatome testing marked with a water-soluble pen. The researchers utilised the method of using participant's finger breadth to establish dermatome testing sites (Gross et al 2015) the dermatome testing sites were based on Keegan and Garrett's dermatome map (Keegan & Garrett, 1948) see Figure 1. From this point forth, the spinal levels will be referred to as L2 or L3, respectively and the corresponding dermatome of the vertebral level will be referred to as DL2 or DL3.

Figure not included due to copyright reasons.

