The lumbar vertebra was mobilised using Maitland's vertebral mobilisation method for posterioranterior central vertebral pressures (PACVPs) for four sets of 30 seconds (Pentelka et al 2012) with up to 30s between each, at a grade III amplitude (Maitland et al 2005) and a target rate of 3Hz (Piekarz & Perry 2015) to ensure the total time for testing was less than fifteen minutes in duration, before the opioid system is activated (Beatti et al 2010). Once the fourth 30-second mobilisation had been completed, the researcher pressed stop on the laptop and asked the participant to roll onto their back. Then the next five sets of data were collected following the same procedure implemented for the baseline measures (collected in a different, pre-determined order each time). This process was repeated for the remaining two vertebrae.

Statistical Analysis Plan

A Multivariate Analysis of Variance (MANOVA) for individual levels against baseline and a One-way Analysis of Variance (ANOVA) for the collated (data set reduced to identify effects at either the same vertebral level as treated versus baseline, one, two or three above or below respectively) mobilisation effect including Tukey post hoc tests for both were conducted using IBM SPSS statistics 25, p values less than 0.05 were defined as acceptable. Effect sizes identifying Cohens d (Large 0.8, Medium 0.5, and Small 0.2) and Magnitude Based Inferences (MBI) were also calculated for each a more comprehensive analysis of the data.

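### Tukey's all-pairs test is valid but conservative when baseline is the only comparator the SAP names; a many-to-one test would be a cheap gain

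*Combined protocol and SAP*

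**What the plan says.** The Statistical Analysis Plan sets out two analyses. The first is "A Multivariate Analysis of Variance (MANOVA) for individual levels against baseline". The second is a one-way ANOVA on a collated data set, arranged by distance from the treated level: "data set reduced to identify effects at either the same vertebral level as treated versus baseline, one, two or three above or below respectively". The post hoc procedure is the same for each: "including Tukey post hoc tests for both were conducted using IBM SPSS statistics 25". The threshold is "p values less than 0.05 were defined as acceptable".

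The Study Design section describes a "randomised, single-blind, repeated measures, cross-over design", and twenty people took part. The Data Collection section randomises the order in which the lumbar levels are mobilised. Baseline is always measured first, before any mobilisation. No level-versus-level or distance-versus-distance contrast is named anywhere, and no reason is given for testing all pairs.

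**The concern.** Tukey's procedure protects every pairwise difference at once. If the question is only whether each condition differs from one reference, part of that protection goes to pairs nobody has asked about, and the intervals for the wanted comparisons are wider than they need to be. A many-to-one procedure holds the same 5% familywise error over the comparisons with baseline and uses a smaller critical value.

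With 20 participants and no sample-size calculation in the documents, precision is scarce. What is at stake is power for detecting a change from baseline at each dermatome, which is how the plan as worded judges how far the effect extends. The change needs no new data.

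**Working it through.** The plan gives no power, target difference, standard deviation or interval width, so there is no figure of its own to reproduce.

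**Inputs**
- 20 participants (Sample and Inclusion Criteria).
- 4 conditions: baseline and three mobilisations (Data Collection).
- 5 dermatome sites per condition: DL2, DL3, DL4, DL5 and S1 (Data Collection and Figure 1 legend).
- Alpha 0.05 (SAP). Sidedness is not stated; both procedures are taken as two-sided.

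**Size of each family**
- Per dermatome: 4 × 3 / 2 = 6 pairs, of which 3 involve baseline.
- Collated: mobilising L3, L4 and L5 and testing five sites gives distances from −3 to +3, holding 20, 40, 60, 60, 60, 40 and 20 readings (300 in all). There are also 20 × 5 = 100 baseline readings. With above and below kept apart that is 8 groups: 8 × 7 / 2 = 28 pairs, of which 7 involve baseline.

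**Critical values**

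Tukey is the 0.95 quantile of the studentized range divided by √2. Dunnett is the two-sided many-to-one multivariate t value, by numerical integration. Both use the same standard error, so the ratio of critical values is the ratio of interval widths.

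| | Tukey | Dunnett | Unadjusted t | Dunnett / Tukey |
|---|---|---|---|---|
| Per dermatome, df = 3 × 19 = 57 | 2.646 | 2.413 | 2.002 | 0.912 |
| Collated, df = 400 − 8 = 392 | 3.047 | 2.675 | 1.966 | 0.878 |

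Per dermatome, the intervals are 1 − 0.912 = 8.8% narrower. The precision gain equals (2.646 / 2.413)² = 1.20, about 20% more participants. With an independent-groups error (df 80 − 4 = 76) the values are 2.627 and 2.397, nearly the same ratio. Bonferroni over the three baseline contrasts, which is Holm's first step, gives 2.467 at df 57, also below Tukey.

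**Share of the adjustment spent on unnamed pairs**

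This is the part of Tukey's increase over the unadjusted t that goes beyond Dunnett:
- Per dermatome: (2.646 − 2.413) / (2.646 − 2.002) = 0.233 / 0.644 = 36%.
- Collated: (3.047 − 2.675) / (3.047 − 1.966) = 0.372 / 1.081 = 34%.

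**Power, per dermatome, from the noncentral t at df 57**
- A contrast with 70% power under Tukey has about 77% under Dunnett.
- At the SAP's medium benchmark (d = 0.5, not a stated target), Tukey against Dunnett is 34.9% against 43.6% with an assumed within-person correlation of 0.5, and 59.7% against 68.2% with 0.7.

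**Error actually held over the three baseline contrasts**

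Using 2.646, the chance of at least one false positive at a dermatome is about 2.8%; using 2.413 it is 5%. Across five dermatomes, assuming independent sites and all nulls true, that is 1 − 0.972⁵ = 13% against 1 − 0.95⁵ = 23%.

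**The case against.** **Tukey is not wrong.** With its assumptions met it controls type I error for the baseline contrasts, and writing it into the plan is itself a specification of all-pairs testing. This stands: the point concerns efficiency. A reader might infer that the plan contains a statistical error here, and the documents do not support that.

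**The collated sentence is ambiguous.** The reference to baseline is attached to the same-level effect; the other distances follow without a comparator. A study of extent might well want distances or levels compared with each other, and all-pairs testing would then be defensible. This stands in part. Baseline is only implied for the other distances, but the plan names no other comparator.

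**Randomisation protects the between-level contrasts.** Because only the order of mobilised levels is randomised and baseline always comes first, contrasts with baseline are mixed with time and repeated testing. This is a good reason to keep the between-level contrasts as a declared set. It does not make an all-pairs adjustment the right one for the baseline comparisons.

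**The share lost is easily overstated.** Counting pairs, 3 of 6 and 21 of 28 are not against baseline, so a reader might infer that half and three quarters of the adjustment is spent on them. Critical values do not scale with the number of pairs; the share is about a third in both analyses.

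**The error model matters more than the post hoc test.** Standard Tukey and standard Dunnett both assume independent groups. At df 76 and d = 0.5, Tukey's power goes from 15.5% at zero within-person correlation to 60.4% at an assumed 0.7, while moving to Dunnett adds only 6 to 9 points. This stands, and is why the fix takes the contrasts from a within-person model.

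**Conclusion.** A minor, worthwhile improvement. For the comparisons the SAP names, a many-to-one test gives intervals about 9% narrower per dermatome and lifts 70% power to about 77%. This rests on baseline being the comparator of interest, two-sided testing, four conditions in 20 people with complete data, and a common within-person error on 57 df.

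The collated result (3.05 against 2.67) is illustrative only, since it treats 400 readings from 20 people as independent. It also depends on the grouping: Tukey is 14% wider with 100 baseline readings and 19% wider if baseline holds only 20, or 11% to 17% wider if above and below are pooled. The direction is the same in each case, but none of these converts into a number of participants.

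A reader might also infer that the extent of the effect will be understated. The documents do not establish that: the SAP reports Cohen's d and magnitude-based inferences as well, so extent is not judged on Tukey p values alone.

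**What to change.** In the Statistical Analysis Plan, replace the Tukey tests in both analyses with comparisons of each mobilised condition, or each distance group, with baseline, adjusted by a Dunnett-type or Holm method. Take them from a repeated-measures or mixed model with participant as a random effect, not from the independent-groups ANOVA. List any between-level or between-distance contrasts, which are the ones the randomised order protects, as a separate set with its own adjustment. If all pairs really are wanted, keeping Tukey-type adjustment is acceptable provided the plan names those contrasts and says why.

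Costs:
- A different model has to be fitted; this is more than one changed option in the software.
- Between-level pairs lose joint coverage unless they are declared.
- The per-dermatome error over the baseline contrasts rises from about 2.8% to 5%. That is the threshold the plan states, but nothing adjusts across the five dermatomes, so the plan should say how results across sites will be read.
- The SAP is written in the past tense. If the data have already been analysed, the change must be labelled post hoc and the Tukey results reported beside it.

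### The SAP names a One-way ANOVA with Tukey tests for a within-person cross-over, states no repeated-measures error term, and adds MBI with no settings or role

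*Combined protocol and SAP*

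**What the plan says.** The Study Design section describes a "randomised, single-blind, repeated measures, cross-over design". Twenty people each give readings at five dermatome sites (L2 to S1), at baseline and after mobilisation of L3, L4 and L5.

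The Statistical Analysis Plan gives a MANOVA for individual levels against baseline and "a One-way Analysis of Variance (ANOVA) for the collated" data, "including Tukey post hoc tests for both". The collated analysis is meant to "identify effects at either the same vertebral level as treated versus baseline, one, two or three above or below respectively". The only decision rule is "p values less than 0.05 were defined as acceptable". Neither analysis is given a repeated-measures or within-person error term.

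The next sentence adds "Effect sizes identifying Cohens d (Large 0.8, Medium 0.5, and Small 0.2") and then "Magnitude Based Inferences (MBI) were also calculated for each a more comprehensive analysis of the data". This is the only mention of MBI. The plan gives no smallest worthwhile change, standardising SD, probability cut-offs or multiplicity control for it. It does not say whether MBI is descriptive, or which result governs if MBI and Tukey disagree. The 0.2, 0.5 and 0.8 labels are attached to Cohen's d, not to MBI.

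**The concern.** The title asks about "The Immediate Extent of the Hypoalgesic Effect", so the answer is in effect a list of which dermatomes, or which distances from the treated level, changed. Two features of the plan bear on that list.

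- **Error term.** A One-way ANOVA treats the conditions as independent groups. When the same people supply every condition, person-to-person variation stays in the error term although it cancels from the differences. The Tukey threshold is then too wide and the extent can be understated.
- **MBI.** This is an inference method, not just an effect size. Without settings or a role, nothing in the plan prevents a 'possible' or 'likely' label from being reported as an effect at a site where the Tukey test is not significant. If that happened, the extent could be overstated by an amount the plan does not fix.

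**Working it through.** The plan states no power, sample-size basis or MBI error rate, so there is no figure to reproduce.

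**Inputs from the documents:** n = 20; four conditions (baseline plus three levels); five sites, hence 3 × 5 = 15 contrasts with baseline; alpha 0.05; Tukey.

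**Assumptions (not in the documents):** normal data, a common SD of 1 and equal within-person correlation ρ across conditions. For MBI: a threshold δ of 0.2 or 0.5 SD; a limit on the opposite-direction chance of 0.5%, 5% or 10%; and labels 'possible' (>25%), 'likely' (>75%) and 'very likely' (>95%).

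**Step 1: Tukey critical difference at one site.** This is q × √(MSE/n).
- Within-person: q = 3.743 (57 df) and MSE = 1 − ρ. At ρ = 0.5 it is 3.743 × √(0.5/20) = 0.59 SD; at ρ = 0.7 it is 3.743 × √(0.3/20) = 0.46 SD.
- Between-group: q = 3.715 (76 df) and MSE = 1. It is 3.715 × √(1/20) = 0.83 SD whatever ρ is.

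**Step 2: power for a true 0.5 SD reduction at all three levels.** The true standard error of a contrast is √(2(1 − ρ)/20), which is 0.224 at ρ = 0.5 and 0.173 at ρ = 0.7.
- Within-person: the critical t is 3.743/√2 = 2.65. The standardised effect is 0.5/0.224 = 2.24 or 0.5/0.173 = 2.89. Power is 35% and 60%.
- Between-group: the observed difference must exceed about 0.83 SD, which is (0.83 − 0.5)/0.224 ≈ 1.5 or 0.33/0.173 ≈ 1.9 standard errors above the truth. Simulation, which allows for the estimated error variance, gives 9% and 5%.
- At ρ = 0 the two agree at 15%. The loss comes entirely from ignoring the pairing.

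**Step 3: false MBI labels for one paired contrast, no true effect.** With mean reduction m and standard error SE on 19 df, the chance of a reduction beyond the threshold is P(T > (δ − m)/SE). The chance of an increase beyond it is P(T < (−δ − m)/SE). A reduction is labelled when the first exceeds the cut-off and the second is below the limit.

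Hand check at ρ = 0.5, δ = 0.2, SE = 0.224: under the 5% limit, at least 'possible' needs m > 1.729 × 0.224 − 0.2 = 0.187, or 0.84 SE, which has probability about 20%. Simulation gives 21%.

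| Threshold; opposite-direction limit; label | ρ = 0.5 | ρ = 0.7 | ρ = 0.9 |
|---|---|---|---|
| 0.2 SD; 10%; at least 'possible' | 32% | 31% | 9% |
| 0.2 SD; 5%; at least 'possible' | 21% | 25% | 9% |
| 0.2 SD; 0.5%; at least 'possible' | 3.9% | 6.4% | 8.5% |
| 0.2 SD; 5%; 'likely' | 5.9% | 3.5% | 0.4% |
| 0.5 SD; 5%; at least 'possible' | 6.1% | 1.4% | about 0 |
| 0.5 SD; 5%; 'likely' | 0.2% | about 0 | about 0 |

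At 0.2 SD with the 5% limit, 'very likely' is at most 1.2% over ρ from 0 to 0.9. For comparison, an unadjusted t-test falsely finds a reduction 2.5% of the time, and a within-person Tukey contrast about 0.5% (half of its two-sided 1.05%).

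**Step 4: reach of these figures.** They apply to one site with one reading per person per condition. The collated offsets pool 60 post-mobilisation readings for the same level, one above and one below, 40 for each two-level offset and 20 for each three-level offset (3 × 60 + 2 × 40 + 2 × 20 = 300 = 15 × 20). The Step 3 rates therefore do not transfer to the distance analysis.

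**Step 5: family.** Even with a within-person term, Tukey applied separately at each site leaves an 11% to 14% chance of at least one false call over the 15 baseline contrasts (11% with between-site correlation 0.5, 13% to 14% with independent sites).

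**The case against.** The only stated decision rule is the 0.05 p-value with Tukey. MBI follows in a separate sentence alongside Cohen's d, as something also calculated, which most naturally reads as supplementary. A reader might infer that MBI decides which sites responded, or that it has inflated the reported extent. The documents say neither, so this part of the objection stands.

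The direction is open as well. High false-label rates require counting 'possible' as a positive finding, which the plan never does, and strict settings make fewer false calls than an ordinary t-test. Every MBI setting above is assumed, and about 32% is the largest value on the grid tried, not a bound. This also stands.

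A reader might further infer that the analysis was certainly run with a between-group error term. The plan does not say that. It calls the design repeated measures and leaves the error term unstated. 'One-way' is applied to the collated analysis, while the individual-level analysis is a MANOVA with no detail. The 9% and 5% figures therefore describe what follows if a One-way error term is used at a site.

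Finally, the error-term and family problems would exist without MBI. That is true, but they belong together in the remedy: writing down MBI settings alone would leave the extent resting on tests that may ignore the pairing.

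**Conclusion.** The point holds as a weakness in the choice and specification of methods, not as a demonstrated error in the results. The named analysis does not match the within-person design. If its One-way error term is used, most of the power is lost: at ρ = 0.7, about 5% instead of 60% for a 0.5 SD reduction at one site. MBI is an added inference method whose false-label rate the plan leaves undefined, from near 0% to about 32% per paired contrast over the settings tried. Whether it would widen or narrow the reported extent cannot be settled from the documents. The sizes rest on assumed normal data, equal correlations and the listed MBI rules. The mismatch with the design and the missing MBI settings and role do not depend on those assumptions.

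**What to change.** - Fit a repeated-measures (within-person) model and report each baseline contrast as a mean difference in cm on the VAS, with a multiplicity-adjusted 95% confidence interval.
- Name the family that the adjustment covers. Tukey within one site does not control error over the five sites or over both analyses.
- Base every statement about affected dermatomes or distances on those contrasts. For the distance analysis, the model must also allow for several readings from one person at the same offset.
- Do not use MBI for inference. Drop it, or label it descriptive and state its threshold, standardising SD and cut-offs.

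**Cost.** No new data are needed. MBI labels are lost or demoted, and fewer sites may be called positive. If all 15 contrasts are controlled by Bonferroni, the critical t rises from 2.65 to 3.06 (57 df). Within-person power for a 0.5 SD reduction then falls from 35% to 22% at ρ = 0.5 and from 60% to 44% at ρ = 0.7. Both remain well above the 9% and 5% of a between-group Tukey test.
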